3.1.1.1 Adjudicated adverse events

An independent adjudication committee is constituted to provide an independent, external, systematic, and unbiased assessment of blinded data to confirm diagnosis of 1) Investigator-reported non-fatal myocardial infarction, non-fatal stroke (hemorrhagic, ischemic, embolic), as well as cardiovascular deaths and 2) Investigator-reported malignancies during the Phase 3 trials. The committee will operate in accordance with an Adjudication Committee Charter/Manual of Operations, which will also provide detail on specific information the committee requires to enable a thorough adjudication.

3.1.2 Laboratory variables

Blood and urine samples for determination of clinical chemistry, haematology and urinalysis parameters will be taken at times detailed in the CSP, and will be assessed in a central laboratory. The parameters outlined in Section 5.2.5, Tables 3 and 4 of the CSP will be collected. Laboratory data is to be reported in SI units. Eosinophils data will be presented in both SI and conventional units (cells/ μ L) in summaries.

Changes in haematology and clinical chemistry variables between baseline and each subsequent assessment will be calculated. For values recorded with a leading greater than or less than ('>', '<') symbol, the reported numeric value will be used for analysis and the value

with the symbol will be included in the listings, unless otherwise specified. For example, a value of <0.01 will be analysed as 0.01 and listed as <0.01.

Absolute values will be compared to the relevant reference range and classified as low (below range), normal (within range or on limits) or high (above range). The central laboratory ranges will be used for laboratory variables. All absolute values falling outside the reference ranges will be flagged.

Urinalysis data will be categorised as negative (0), positive (+), or strongly positive (++, +++, or >+++) at each time-point.

For the purposes of haematology, clinical chemistry and urinalysis shift tables, baseline will be defined as the latest non-missing assessment prior to first IP dose date, and maximum or minimum value post-baseline will be calculated over the entire post-baseline period, including the post-treatment unscheduled assessments.

For the liver function tests: Aspartate Aminotransferase (AST), Alanine Aminotransferase (ALT), Alkaline phosphatase, Gamma-GT (GGT) and total bilirubin (TBL), the multiple of the central laboratory upper limit of the normal (ULN) range will be calculated for each data point.

$$\text{Multiple} = \text{Value} / \text{ULN}$$

For example, if the ALT value was 72 IU/L (ULN 36) then the multiple would be 2.

Patients who meet any of the following criteria at any point during the study will be flagged:

- AST $\geq 3 \times$ ULN
- ALT $\geq 3 \times$ ULN
- TBL $\geq 2 \times$ ULN

In addition to the safety laboratory tests, immunoglobulins and T cell, B cell and NK cell (TBNK) flow cytometry are collected for adolescent patients.

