- a Medical and asthma history, AEs and concomitant medications will be linked to the predecessor study to create a complete and continuous record for the patient.
 - b Assessments done at the EOT visit of the predecessor study do not need to be repeated at Visit 1 of this study, as the data will be duplicated between study databases (see Section 4.1.1).
 - c All visits are to be scheduled from the date of randomization but not from the date of previous visit
 - d Detailed schedule for serum chemistry tests provided in Section 5.2.5, Table 3 and Table 4
 - e For WOCBP, urine HCG test to be done at center on each treatment visit before IP administration.
 - f PK, ADA and nAb samples to be collected before IP administration.
 - g FSH test done only for female patients <50 years who have been amenorrheic for >12 months to confirm postmenopausal status
 - h In case of anaphylaxis additional samples to be taken (see Section 6.9)
 - i Unscheduled visits may be initiated as needed, and additional assessments performed at these visits, at the discretion of the Investigator
 - j IPD visit should be completed within 4 weeks (+7 days) after last scheduled site visit
 - k Refer to CRF for specific CV history to be collected
 - l All patients transitioning from ZONDA into this study are exempt from performing the post-BD assessments. The pre-BD measurement from EOT for ZONDA patients will serve as the first pre-BD measurement for these patients in BORA.
 - m Patients transitioning into Study D3250C00037 will complete EOT assessments for this study at the same visit during which they transition. Patients who are asked to transition into this study by the Investigator must do so at the next odd-numbered visit (ie, Visit 5, 7, 9, or 11) once the study has started at their site (see Section 4.2).
- D Days; EOT End-of-treatment; FU Follow-up; R Randomization; V Visit; UNS Unscheduled; W Week; IPD Premature IP Discontinuation

Table 2A Study Assessments Schedule – Adolescents: Weeks 0 to 64

Assessment/ activity	Refer to	Treatment																IPD _i	UNS _h	
		Visit window (days) ^c																		
		V1 w0	V2 w4	V3 w8	V4 w12	V5 w16	V6 w20	V7 w24	V8 w28	V9 w32	V10 w36	V11 w40	V12 w44	V13 w48	V14 w52	V15 w56	V16 w60			V17 w64
		±0	±2	±3	±3	±3	±3	±3	±3	±3	±3	±3	±3	±3	±3	±3	±7	±7	N/A	
Inclusion/exclusion criteria	3.1/3.2	X																		
Informed consent+assent	10.4	X																		
Medical and asthma history	5.2.1	X ^a																		

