4.1 Enrolment period

4.1.1 Randomization (Visit 1)

Each potential patient or parent/legal guardian (as applicable) will provide written informed consent prior to any study specific procedures and undergo assessments applicable for the visit (see [Table 1](#) or [Table 2](#)).

In order to provide sufficient time for patients to consider participation in this study, and to ensure an uninterrupted dosing regimen as patients transition between the predecessor study and this study, patients will be provided with the ICF at/after the visit at which they receive their last dose of IP in the predecessor study and will be asked to sign the ICF at Visit 1 of this study, prior to any study-specific procedures being performed.

Visit 1 of this study will be scheduled to ensure an uninterrupted dosing regimen as patients transition between the predecessor study and this safety extension study. Therefore, if the actual EOT visit in the predecessor study occurs more than 7 days from the scheduled EOT visit, the patient will not be eligible to enrol in this study. The End-of-Treatment (EOT) visit for the predecessor study and Visit 1 for this study will occur on the same day and will include the first dose of IP for this study. If IP cannot be administered at this visit, the patient will not be eligible for enrolment in this study.

As Visit 1 coincides with the EOT visit of the predecessor study, repeated assessments (see [Table 1](#) and [Table 2](#)) are not required, as data will be duplicated programmatically between the 2 study databases, as applicable. As electronic patient-reported outcome (PRO) devices were used to capture ACQ6, AQLQ(S)+12, WPAI+CIQ, EQ-5D-5L in the predecessor studies, the patient does not need to complete the paper versions of these at Visit 1 of this safety extension study.

Registration of patient's enrolment via IWRS/IVRS should occur on day when other Visit 1 procedures are done.

Visit 1 assessments are primarily concerned with confirmation of the patient eligibility for the extension study

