5.2.5 Safety laboratory tests

Safety laboratory tests (list provided in [Table 3](#) and [Table 4](#)) will be performed in a central laboratory. For information on methods of collection, assessment, labelling, storage and shipment of samples, please refer to the separate Laboratory Manual. Safety samples will be collected in accordance with the schedules provided in [Table 1](#) or [Table 2](#).

Hematology and urinalysis will be assessed in line with the schedules provided in [Table 1](#) or [Table 2](#). A detailed schedule of the chemistry tests is presented in [Table 3](#) and [Table 4](#). Visit 1 of this study is to be combined with the EOT visit of the predecessor study (see [Section 4.1.1](#)), therefore safety laboratory tests performed at the EOT visit in the predecessor study will be considered as baseline for this safety extension study. NB: As the required list of safety laboratory tests at Visit 1 of this safety extension study differs from those collected at EOT of the predecessor studies, the additional parameters required for this study (ie, those not required at the EOT visit of the predecessor study) will only be reported in this study to avoid duplicate reporting. Refer to the separate Laboratory Manual for more details.

Laboratory results should be reviewed by the Investigator/authorized delegate and evaluated for abnormalities. Any laboratory abnormalities considered significant in the Investigators'/authorized delegate's judgement should be reported as described to in [Section 7.1.3](#).

The copy of the laboratory results report should be signed and date by Investigator and retained at the study center.

Table 3 List of safety laboratory tests

Serum chemistry		Hematology	Urinalysis
Alkaline phosphatase	Gamma-GT (gamma-glutamyl transpeptidase)	Hematocrit	Appearance
ALT (alanine aminotransferase)	Glucose	Hemoglobin	Blood
AST (aspartate aminotransferase)	Phosphorus	Mean corpuscular volume (MCV)	Colour
BUN (blood urea nitrogen)	Potassium	Platelet count	Glucose
Calcium	Sodium	Red blood cell (RBC) count	Ketones
Chloride	Total bilirubin	WBC count with differential ^a	Microscopy including WBC/high power field (HPF), RBC/HPF
CO ₂ (carbon dioxide)	Total cholesterol		pH
Creatinine	Uric acid		Specific gravity
Serum concentration ^b			

^a Eosinophil, basophil and monocyte counts will be redacted from the central laboratory reports

^b For patients who are on theophylline or digoxin (see Section 3.5.2.2)

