2.4 Baseline and change from baseline

In general, the last non-missing value on or prior to the first dose of IP in BORA will be used as the baseline. The last evaluable post-dose record from the predecessor studies will also be

considered in the selection of baseline value for BORA study. If there is no assessment present, then the baseline value will not be imputed and will be set as missing. Exceptions for both pre-bronchodilator (pre-BD) and post-bronchodilator (post-BD) FEV₁ as specified below.

For pre-BD FEV₁, the following hierarchy rules will be applied to derive baseline:

- Step 1: Select values with acceptable quality (acceptable or borderline quality grade) on the same date closest to the first IP dose in BORA. If the assessments are on the same day of the first IP dose, only the assessments on or prior to the IP dose are used.
- Step 2: If there are central and local spirometry assessments on the same day, central spirometry assessments will be used.
- Step 3: If there are multiple assessments with different times, the earliest assessment will be used.
- Step 4: If there are multiple assessments with the same date and time, the value recorded in the BORA study database will be used.

For post-BD FEV₁, the baseline will be derived independently from pre-BD FEV₁ assessments. With exception from Step 2 to select the highest value within central or local spirometry, the same hierarchy rules as explained above will be applied.

Change from baseline will be calculated as the post-baseline assessment value minus the baseline assessment value. If either value is missing, then the change from baseline value will be missing.

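### The laboratory shift-table baseline in SAP 3.1.2 excludes a Visit 1 sample drawn on the dosing day, contrary to SAP 2.4 and protocol 5.2.5

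*SAP*

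**What the plan says.** SAP 3.1.2 has its own baseline rule for the laboratory shift tables: "baseline will be defined as the latest non-missing assessment prior to first IP dose date". The test is on the calendar date, not on whether the sample came before the injection.

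The general rule in SAP 2.4 is that "the last non-missing value on or prior to the first dose of IP in BORA will be used as the baseline". It lists exceptions for pre- and post-bronchodilator FEV₁ only.

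Protocol 5.2.5 states that "safety laboratory tests performed at the EOT visit in the predecessor study will be considered as baseline for this safety extension study". Because the BORA test list is longer than the predecessor one, it adds that "the additional parameters required for this study (ie, those not required at the EOT visit of the predecessor study) will only be reported" in BORA. Protocol 4.1.1 says that the predecessor EOT visit and BORA Visit 1 "will occur on the same day and will include the first dose of IP for this study". Footnote b to protocol Table 1 adds: "Assessments done at the EOT visit of the predecessor study do not need to be repeated at Visit 1 of this study".

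SAP section 6 declares no change from the protocol analyses.

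On a related point, SAP 4.2.5.1 repeats the overall adverse event summary by baseline blood eosinophil count (below 300/µL, or 300/µL and above). SAP 4.2.1, 4.2.2, 4.2.6, 4.2.7 and 4.2.8 use the same cut but specify the predecessor baseline.

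**The concern.** Laboratory variables are one of the primary safety endpoints, and shift tables are a main way of showing them. If the baseline skips the Visit 1 sample and falls back on an older one, the table no longer describes change from the start of BORA treatment. This can mislead in two ways:

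- A value that became abnormal before the first BORA dose, and stayed abnormal, is tabulated as a shift in BORA.
- A value that was abnormal at the older sample, normal at Visit 1 and abnormal again in BORA shows no shift.

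In both cases the by-visit change table, which follows SAP 2.4, would start from a different value, so the study report could disagree with itself on one parameter.

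In SAP 4.2.5.1, the word baseline read through SAP 2.4 means the value at BORA entry. For patients who had benralizumab in the predecessor study, that is an on-drug value, and protocol 1.2 describes the drug as depleting eosinophils. The adverse event subgroups could then differ from those in the disposition and baseline tables.

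**Working it through.** The plan gives no figure to reproduce. The check applies the SAP's study-day formula to one sample under each rule.

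**Inputs.** Study day = (date of assessment − date of first dose) + 1 (SAP 2.3). Visit 1, predecessor EOT and first dose share one date (protocol 4.1.1), and the Visit 1 window is ±0 days (protocol Table 1). I assume the Visit 1 sample is drawn before the injection.

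**Step 1: day of the sample.** Assessment date − first dose date = 0, so study day = 0 + 1 = 1.

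**Step 2: apply each rule.**

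| Source | What qualifies | Day 1 pre-dose sample |
|---|---|---|
| SAP 3.1.2 | Date difference ≤ −1, so Day ≤ 0 | Excluded |
| SAP 2.4 | Up to the first dose, so Day ≤ 1 | Included |
| SAP Appendix A, Tables 4a, 5b, 6c | Week 0 is Day ≤ 1; the next window opens on Day 2 | Week 0 |
| Protocol 5.2.5 | Predecessor EOT tests | Is the baseline |

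The rules differ on Day 1 alone, and Day 1 is the scheduled Visit 1.

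**Step 3: could the sample be dated a day earlier?** Protocol 4.2.3.4 allows blood to be drawn one day before dosing, but only from Visit 2. There are two cases:

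- *Parameters not required at the predecessor EOT visit.* These are sampled under BORA, and patients "will be asked to sign the ICF at Visit 1 of this study, prior to any study-specific procedures being performed" (protocol 4.1.1). The sample cannot predate Visit 1, so its exclusion is certain.
- *Parameters carried over from the predecessor EOT visit.* These are excluded if the sample is dated the day of dosing. If it is dated earlier, both rules select it. The predecessor schedules and draw-date rules are not in the documents, so the share affected runs from none to all.

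**Step 4: which displays are exposed?** SAP 4.2.5.2 plans three kinds: reference-range shift tables, CTCAE white-cell shifts and urinalysis shifts. SAP 3.1 allows no imputation. A patient with no earlier value therefore falls into the missing category in the reference-range tables. The urinalysis table omits that patient, because it needs both a baseline and a post-baseline value. By-visit changes have no separate rule and follow SAP 2.4. Shift plots are not named in the 3.1.2 rule, so on the text they also default to SAP 2.4. It is also unclear whether the excluded Day 1 sample would count towards the post-baseline maximum or minimum.

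**Step 5: scope.** Protocol Table 3 has 8 + 8 = 16 chemistry lines (leaving out theophylline and digoxin levels), 6 haematology lines and 8 urinalysis lines: 16 + 6 + 8 = 30. This is the number of test lines under the rule, not a count of parameters known to change.

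**Eosinophil split.** One SAP section (4.2.5.1) says baseline; five say predecessor baseline.

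**The case against.** The strongest reply is that this is a drafting slip. The author probably meant before the first dose, and the word for date crept in. Appendix A already treats a dosing-day laboratory sample as Week 0, and nothing suggests an intention to discard Visit 1 results, so programmers may have used the SAP 2.4 rule anyway. SAP 2.4 also opens with a general qualifier that leaves room for section-specific rules. The slip is likely, but a specific rule overrides a general one, so the literal text binds whoever programs or checks the tables. Appendix A is further evidence that 3.1.2 is out of line with the rest of the plan.

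Other limits stand. For carried-over parameters the conflict depends on draw dates that cannot be seen. A parameter not required at predecessor EOT may have been measured earlier in that study, and SAP 2.4 allows predecessor records as baseline, so a missing baseline is possible but not established. The SAP does not state a baseline for the shift plots, so their divergence from the tables is an inference. The eosinophil wording is a separate issue and most likely a dropped word, since the 300/µL cut and the five parallel sections point to the predecessor value. It adds no weight to the laboratory point.

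**Conclusion.** The concern holds. SAP 3.1.2 as written conflicts with SAP 2.4 and with the SAP's own Week 0 windows. It also conflicts with protocol 5.2.5 whenever the EOT sample is dated the day of dosing, although SAP section 6 reports no departure from the protocol.

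The difference is exactly one study day, the scheduled Visit 1. Every patient sampled is affected for parameters not required at the predecessor EOT visit, which the protocol does not name. For the rest, the range is none to all. The age of any substitute value, and the number of table entries that would change, cannot be worked out from the documents.

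By-visit values, the liver-threshold flags and the out-of-range listings do not use this baseline and are unaffected. All analyses are descriptive, so no test or error rate is involved. The harm is to the accuracy and consistency of the primary-endpoint shift tables, and it should be corrected.

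**What to change.** In SAP 3.1.2, replace the separate rule with a reference to the Section 2.4 baseline, for example: *baseline is the Section 2.4 value, including a pre-dose sample taken on the day of the first BORA dose*. Shift tables, shift plots and by-visit changes would then share one baseline, and the Day 1 pre-dose sample could not be read as post-baseline.

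In SAP 4.2.5.1, insert the word *predecessor* before the baseline eosinophil count, to match the five other sections.

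The cost is a few words in two SAP sections and a check that the programming matches. No new data are needed.

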3.1.3 Physical examination

Complete and brief physical examinations will be performed at time points specified in Section 4, Tables 1 (adults) and 2A and 2B (adolescents) of the CSP. What is included in the assessment will be dependent on whether the examination is complete or brief, as described in Section 5.2 of the CSP. For the brief physical examination only information on whether the assessment was performed or not is to be recorded.

Each component of the baseline (Visit 1) complete physical examination will be recorded as normal or abnormal. Each component of the follow-up complete physical examinations will be recorded as normal, same as baseline, or new/aggravated.

Any new finding(s) or aggravated existing finding(s), judged as clinically significant by the Investigator, will be reported as an AE.

3.1.4 Electrocardiograms

Twelve-lead electrocardiogram (ECG) measurements will be recorded in accordance with schedule provided in Tables 1 (adults) and 2A and 2B (adolescents) of the CSP.

The outcome of the overall evaluation is to be recorded as normal/abnormal in the eCRF, with any abnormalities being recorded as not clinically significant or clinically significant.

3.1.5 Vital signs

Pre-dose vital signs (pulse, systolic blood pressure, diastolic blood pressure, respiration rate and body temperature) will be obtained in accordance with schedule provided in Section 5.2, Tables 1 (adults) and 2A and 2B (adolescents) of the CSP.

Changes in vital signs variables between baseline and each subsequent scheduled assessment will be calculated.

Absolute values will be compared to the relevant reference range (Table 1) and classified as low (below range), normal (within range or on limits) or high (above range). All values (absolute and change) falling outside the reference ranges will be flagged.

Table 1 Vital signs reference ranges

| Parameter | Standard Units | Lower Limit | Upper Limit |
|--------------------------------|----------------|-------------|-------------|
| Diastolic Blood Pressure (DBP) | mmHg | 60 | 120 |
| Systolic Blood Pressure (SBP) | mmHg | 100 | 160 |
| Pulse Rate | Beats/min | 40 | 120 |
| Respiratory Rate | Breaths/min | 8 | 28 |
| Body Temperature | Celsius | 36.5 | 38 |
| Weight | kg | 40 | 200 |

Body mass index (BMI) will be calculated from the height and weight as follows:

$$\text{BMI (kg/m}^2\text{)} = \text{weight (kg)} / (\text{height (m)})^2$$

3.2 Efficacy outcome variables

3.2.1 Exacerbation

3.2.1.1 Annual exacerbation rate

The analysis is based on exacerbation events reported by the investigator in the eCRF. The exacerbation events will be categorised according to their onset date into on-study, on-treatment and post-treatment periods following the same algorithms used to classify study periods for AEs in Section 3.1.1 above. Similarly, for the analysis of adolescent data at Week 56 visit, only on-treatment exacerbations will be included in the adult completion analysis phase.

For the production of summary statistics, the annual exacerbation rate in each treatment group will be calculated for on-treatment, post-treatment and on-study periods using the time-based approach.

- Annual Exacerbation Rate (on-treatment)=Total number of on-treatment exacerbations *365.25/Total duration of on-treatment follow-up within the treatment group (days)
- Annual Exacerbation Rate (post-treatment)=Total number of post-treatment exacerbations *365.25/Total duration of post-treatment follow-up within the treatment group (days)
- Annual Exacerbation Rate (on-study)=Total number of on-study exacerbations *365.25/Total duration of on-study follow-up within the treatment group (days)

Where the durations of follow-ups for on-treatment, post-treatment and on-study periods will follow the definitions of corresponding study periods in the AE Section 3.1.1.

3.2.1.2 Time to first asthma exacerbation

Time to first asthma exacerbation will only be calculated for the patients who were randomised to placebo in the predecessor studies with start of exacerbation during the on-treatment period, and is calculated as follows:

$$\text{Start Date of first asthma exacerbation} - \text{date of first dose} + 1.$$

The time to first asthma exacerbation for patients who do not experience an asthma exacerbation during the treatment period will be censored at their end of on-treatment period as defined in AE Section of 3.1.1.

